1.2 Rationale and Significance

Symptom burden in patients with incurable lung and gastrointestinal cancer and their families: Patients with incurable solid tumors experience high rates of both physical and psychological distress.^{16,17} Symptoms such as pain, fatigue, dyspnea, and nausea lead to a poor QOL and are associated with high rates of depression and anxiety.¹⁸ The family members of these patients also frequently experience emotional, physical and financial distress when caring for loved ones with incurable cancers.^{19,20} Despite advances in cancer care, life expectancy remains limited for

patients with incurable malignancies, such as lung and non-colorectal gastrointestinal (GI) cancer, which account for more than half of cancer-related deaths in men and one-third in women.²¹⁻²⁴ These patients have a median survival of less than one year and often receive limited benefit from chemotherapy, usually with progression of disease after only a few months of treatment.²⁵ While chemotherapy may improve symptoms, the impact on QOL is less clear as patients also experience marked side effects and toxicities from anti-cancer therapies, causing physical and emotional suffering.⁴ Impairments in QOL and mood not only compromise the wellbeing of patients with incurable cancer and their families, but also predict lower rates of survival.²⁶⁻²⁸ Typically, patients with incurable lung and non-colorectal GI cancers experience a high symptom burden, which begins at the time of diagnosis, persists throughout the course of disease, and intensifies near the end-of-life.²⁹ Interventions should occur early in the course of incurable disease and demonstrate a meaningful impact on the suffering of patients with poor prognosis cancers and their family caregivers.

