1.3 Hypotheses

Aim 1: To determine the efficacy of early, integrated palliative care (PC) on patient and family caregiver reported outcomes in those with newly diagnosed incurable lung or non-colorectal gastrointestinal cancer.

- Hypotheses 1: Compared to patients receiving standard care (SC), patients receiving early PC will (1) experience improved QOL and fewer depressive symptoms; and (2) report a more accurate understanding of their terminal illness and the goals of care.
- Hypotheses 2: Compared to family caregivers in the SC arm, family caregivers of patients receiving early PC will (1) experience improved QOL and fewer depressive symptoms throughout the course of the patient's illness; and (2) report a more accurate understanding of the patient's terminal illness and the goals of care.

Aim 2: To assess the impact of early, integrated PC on quality of EOL care and resource utilization in patients with newly diagnosed incurable lung or non-colorectal gastrointestinal cancer

- Hypotheses: Compared to patients receiving SC, patients receiving early PC will (1) receive higher quality EOL care (i.e., less chemotherapy in the last 14 days of life, greater utilization of hospice services, and/or length of stay in hospice > 3 days); (2) experience less hospital and ICU days and (3) have at least the same survival as patients receiving standard care

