4.6 Stratification Factors

4.6.1 Tumor type: lung vs. esophageal/gastric vs. hepatic/biliary/pancreatic/unknown primary

4.6.2 Family caregiver participation: yes vs. no.

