4.7 Study Arm Assignments

4.7.1 The factors defined in Section 4.4 will be used as stratification factors.

4.7.2 After the patient has been registered into the study, the values of the stratification factors will be recorded, and the patient will be assigned to one of the following study groups using the Pocock and Simon dynamic allocation procedure⁵⁵ which balances the marginal distributions of the stratification factors between the two groups.

- Early palliative care
- Standard oncology care

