7.4 Duration of Follow-Up

Survival follow-up will be every 4 months from week 24 until death or up to 3 years (with chart abstraction at death, per section 6.4). Chart abstraction will be performed at year 1, 2, and 3 from enrollment, per section 6.4.

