11.4 Supplementary Analysis Plans

11.4.1 Secondary Endpoints

11.4.1.1 The efficacy of early integrated palliative care (PC) on patient reported outcomes in patients with newly diagnosed incurable lung or non-colorectal gastrointestinal cancer will be assessed by analyzing:

1. Change in QOL on the FACT over time
2. Rate of depressive symptoms as per HADS at 12 weeks and over time
3. Rate of anxiety symptoms as per HADS at 12 weeks and over time
4. Change in illness understanding over time

11.4.1.2 The efficacy of early integrated palliative care (PC) on family caregiver reported outcomes in those with newly diagnosed incurable lung or non-colorectal gastrointestinal cancer will be assessed by analyzing:

1. Change in QOL on the SF-36 over time
2. Rate of depressive symptoms as per HADS at 12 weeks and over time
3. Rate of anxiety symptoms as per HADS at 12 weeks and over time
4. Change in illness understanding over time

11.4.1.3 The impact of early, integrated PC on quality of EOL care and resource utilization in patients with newly diagnosed incurable lung or non-colorectal gastrointestinal cancer will be assessed by analyzing:

1. Rate of referral, enrollment and length of stay on hospice
2. Location of death
3. Number of hospital and ICU admissions and days
4. Chemotherapy and radiation administration
5. Overall survival

11.4.1.4 Concordance between patient and family caregiver report of prognosis/curability.

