11.4.2 Secondary Analysis

We will adopt the gatekeeping procedure for the primary analysis of efficacy of early PC on patient reported outcomes, the secondary analysis of efficacy of early PC on family caregiver reported outcomes, and the secondary analysis of impact of early PC on quality of EOL care and resource utilization. Therefore, they will be tested at the 5% significance level in sequence, and the subsequent analysis (hypothesis testing) will only be carried out if the previous analysis is statistically significant. Otherwise, subsequent analysis will be descriptive in nature. Multiplicity will not be adjusted for other secondary analyses, hence, statistically significant findings from secondary analyses are exploratory in nature and therefore shall be interpreted as such. Descriptive statistics and graphical approaches will form the basis for most secondary analyses.

- 11.4.2.1** To assess the changes in QOL over time among patients, generalized linear model with repeated measures will be used for comparison between treatment arms. To compare rates of psychological distress between treatment arms, we will transform the HADS score into a dichotomous outcome with categories reflecting the presence or absence of clinically significant depression and anxiety. We will then use generalized linear models with repeated measures to assess the association between the presence of depression/anxiety and study arm, using risk difference and relative risk to compare proportions between the study arms. To compare the illness understanding, we will analyze each item of the PTPQ separately using the appropriate test to determine the significance of the between-group differences. To assess additional measures of family caregiver perceptions of quality of death, we will employ the Jonckheere-Terpstra test, which is appropriate for contingency tables with ordinal data.
- 11.4.2.2** To assess the changes in QOL among family caregivers, we will use the similar approach as for QOL among patients. Change in the total score and subscales will be compared with generalized linear models with repeated measures. Analysis of psychological distress and illness understanding will be the same as above.

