- 11.4.2.3** To assess differences in quality of EOL care, we will use Fisher's exact test to determine the association between the composite EOL care measure categories and study arm and a comparison of rates between the groups based on the risk difference and relative risk. To assess the difference in resource utilization, we will also compare days on hospice and in the hospital and ICU using the Mann-Whitney U test. To compare patient survival, we will use Kaplan-Meier estimates, testing the difference between the curves with the log-rank test.
- 11.4.2.4** To assess the concordance between patient and family caregiver report of prognosis/curability, we will analyze each of the primary and secondary endpoints using the matched-pair subset. Simple tests such as paired *t*-test, Wilcoxon signed-rank test, and generalized linear models for matched pair data will be utilized.

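### The survival hypothesis is that early palliative care is no worse, but the plan offers only a log-rank test of difference, with no hazard ratio, confidence interval, margin or reading rule

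*Combined protocol and SAP*

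**What the plan says.** - **Hypothesis.** The third part of the Aim 2 hypothesis (Section 1.3) is that PC patients will "have at least the same survival as patients receiving standard care". This is a not-worse statement.
- **Endpoint.** Section 11.4.1.3 lists "5. Overall survival" last among the end-of-life and resource-use endpoints.
- **Analysis.** Section 11.4.2.3 gives one sentence: "To compare patient survival, we will use Kaplan-Meier estimates, testing the difference between the curves with the log-rank test". The same paragraph names risk difference and relative risk for end-of-life care, but no effect measure for survival.
- **Testing order.** Under Section 11.4.2 this family comes third, after patient-reported and caregiver-reported outcomes, each tested at 5%. If an earlier step is not significant: "Otherwise, subsequent analysis will be descriptive in nature".
- **Allocation.** Section 4.6 stratifies on "Tumor type: lung vs. esophageal/gastric vs. hepatic/biliary/pancreatic/unknown primary" and on caregiver participation. The dynamic allocation in Section 4.7 "balances the marginal distributions of the stratification factors between the two groups". Section 11.4.2.3 does not say whether the survival test uses these factors.
- **Follow-up and prognosis.** Section 7.4: "Survival follow-up will be every 4 months from week 24 until death or up to 3 years". Section 1.2: "These patients have a median survival of less than one year".

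**The concern.** The log-rank test takes equal survival as its null hypothesis. Rejection in favor of PC would support the Aim 2 statement. This could happen, since Section 1.1 reports that the earlier single-institution trial found survival longer by over two months. Rejection against PC would refute the statement. Everything in between leaves it unresolved unless there is an interval showing how large a survival loss the data exclude, and the plan provides none.

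The other parts of Aim 2 expect less chemotherapy near death and fewer hospital and ICU days. The survival clause is the reassurance that these changes do not shorten life. As written, a non-significant p-value could be presented as that reassurance. If an earlier gate fails, only Kaplan-Meier estimates are specified, with no interval for the size of the difference.

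**Working it through.** **What the plan provides.** It states no event count, power or margin for survival. Its only sample size calculation (Section 11.2.1) is for the FACT and reproduces: difference 4, SD 11.87, two-sided 5% and 80% power give 139 per arm against 140 stated, and 140/(1 − 0.30) = 200 per arm. From this only the total of 400 patients, 1:1, is needed here.

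**Inputs.** 400 patients (Section 11.2.1); follow-up to 36 months (Section 7.4); median survival under one year (Section 1.2). *Assumed:* exponential survival, median 6 to 12 months, 0 to 10% loss, with lost patients contributing no deaths.

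**Step 1, deaths.** Deaths = 400 × (1 − loss) × (1 − 0.5^(36/median)).

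| Median (months) | No loss | 10% loss |
|---|---|---|
| 6 | 394 | 354 |
| 9 | 375 | 338 |
| 12 | 350 | 315 |

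**Step 2, precision.** SE(log HR) = 2/√deaths = 0.101 (394 deaths) to 0.113 (315). The CI factor is exp(1.96 × SE) = 1.22 to 1.25. Any observed HR against PC up to about 1.22 to 1.25 therefore gives p > 0.05. At that boundary the upper 95% limit is the square of the factor, about 1.48 to 1.56.

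**Step 3, chance of a non-significant result when PC survival is worse.** P = Φ(1.96 − ln HR/SE) − Φ(−1.96 − ln HR/SE).

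| True HR (PC vs. standard) | 394 deaths | 350 deaths | 315 deaths |
|---|---|---|---|
| 1.15 | 72% | 74% | 76% |
| 1.20 | 56% | 60% | 63% |
| 1.25 | 40% | 45% | 49% |
| 1.30 | 26% | 31% | 36% |

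**Step 4, chance that the test supports the hypothesis.** If survival is truly equal, so that the hypothesis is true, PC is found significantly better 2.5% of the time. Power for superiority reaches 80% only at HR = exp(−2.80 × SE) = 0.73 to 0.75.

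**Step 5, stratification.** This was simulated with 200 per arm, 36 months, no loss, HR 1.20 within each tumor stratum and 4,000 runs. *Assumed* tumor shares, in the order of Section 4.6.1, are 50/15/35%. The Monte Carlo standard error is about 0.8 percentage points.

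| Assumed medians by tumor group (months) | Unstratified test misses | Stratified test misses |
|---|---|---|
| 12/9/6 | 63% | 59% |
| 12/8/4 | 68% | 59% |

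Independent repeats gave 63 to 64% against 59%, and 66 to 67% against 57 to 58%. Caregiver participation was not simulated.

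**Step 6, what a margin could achieve.** Power at a true HR of 1.0 is Φ(ln(margin)/SE − 1.96): 51 to 60% for a margin of 1.25, and 64 to 74% for 1.30. These margins are illustrations only.

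**The case against.** The case for leaving the plan alone has five parts.

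1. **Only a background sentence is at odds.** The operative objective (Section 2.2.3) is to assess impact, the endpoint is simply overall survival, and the analysis compares it. This is true, and it is why rewording the hypothesis is an acceptable remedy. But the hypothesis is stated, and readers will hold the result against it.

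2. **A CI without a margin gives no positive rule.** Read literally, no worse requires an upper limit below 1, which is close to the superiority result already planned. This stands in part. The interval does not turn the analysis into a non-inferiority test. It does show what size of survival loss is excluded and prevents a p-value from standing in for that.

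3. **The harm is conjectural, and non-significance is not always likely.** Nothing in the plan says a null result will be read as equal survival. Non-significance is the more likely outcome only up to a true HR of about 1.22 to 1.25, and falls to 26 to 36% at 1.30. That limit belongs with the claim. Below it, the concern stands.

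4. **Stratification is a separate, smaller point.** Also fair. What the simulation shows is a loss of power, and its size depends on tumor shares and medians that the documents do not give.

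5. **The consequence is small.** Survival is secondary, gated and unpowered, and a hazard ratio could be added at reporting. This limits the weight, but a reading rule chosen after the result is known is worth less than one fixed beforehand.

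**Conclusion.** The concern holds. A not-worse hypothesis is paired with a test of difference, and no section supplies a hazard ratio, interval, margin or reading rule. Unless PC is significantly better, the planned analysis cannot support the hypothesis. Under the assumed 315 to 394 deaths, a non-significant result would occur 56 to 63% of the time at a true HR of 1.20 against PC and 72 to 76% at 1.15, so it offers little reassurance against losses of that size. Failing to stratify would add about 4 to 9 percentage points to the miss rate at HR 1.20 under the assumed tumor mix. The event counts, tumor shares and tumor-specific medians are assumptions. The mismatch itself does not depend on them. The issue should be corrected, but it does not touch the primary endpoint.

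**What to change.** Replace the last sentence of Section 11.4.2.3 with:

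> *Overall survival will be described by Kaplan-Meier estimates and by the hazard ratio (early PC vs. standard care) with 95% CI from a Cox model stratified by tumor type and caregiver participation (Section 4.6). The arms will be compared with a log-rank test stratified by the same factors, within the testing sequence of Section 11.4.2; if an earlier step fails, the hazard ratio and CI are descriptive. A non-significant log-rank test will not be read as showing that survival is no worse; any statement on that hypothesis will rest on the confidence interval.*

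Alternatively, reword the third part of the Aim 2 hypothesis in Section 1.3 as estimation of the survival difference between arms.

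A formal non-inferiority margin is optional. If the team wants one, it should justify it, fix it before any comparative survival analysis, place it in the Section 11.4.2 sequence, and state its modest power.

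**Cost.** Wording only. Both stratification factors are recorded at registration, so no new data, patients or visits are needed. The price is a more cautious survival statement when the result is not significant.

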1.4 Study Design

This study will be a randomized, controlled trial of early PC integrated with standard oncology care versus standard oncology care alone. Patients will be randomized in a 1:1 fashion between study arms. The dynamic allocation procedure was adopted to balance the marginal distributions of stratification: tumor type (lung vs. esophageal/gastric vs. hepatic/biliary/pancreatic/ unknown primary), and family caregiver participation (yes vs. no).⁵⁶ We modeled this study design to be identical to the completed and ongoing trial at the Massachusetts General Hospital (MGH) Cancer Center. We are not randomizing by site (i.e. cluster-randomized design) due to several reasons: (1) Although such a design would reduce contamination effects, it introduces site effects that could also impact outcomes; (2) In both of our prior trials, there was minimal contamination with few patients in the standard care arm referred for PC in the outpatient care setting; and (3) Within Alliance, ensuring equivalent sites across geographical regions with the same PC resources would be challenging. We have also decided not to include an attention control group as the logistical and sample size requirements for a third study arm would be substantial. Additionally, the observed clinical benefits of PC in our previous investigation did not appear to be merely due to increased clinician time with patients and families but related to the expertise of PC clinicians. We anticipate including approximately 20 Alliance sites with a minimum of 10 community sites with an enrollment goal of at least 15 patients per site.

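### Survival, end-of-life and utilisation are tested by arm alone although allocation is balanced on tumor type; if tumor type is prognostic, the tests are valid but mildly conservative and lose some power

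*Combined protocol and SAP*

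**What the plan says.** Allocation. Section 1.4 states: "Patients will be randomized in a 1:1 fashion between study arms". Section 4.7 uses the Pocock-Simon procedure, which "balances the marginal distributions of the stratification factors between the two groups". Section 4.6 lists two factors: "Tumor type: lung vs. esophageal/gastric vs. hepatic/biliary/pancreatic/unknown primary" and "Family caregiver participation: yes vs. no".

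Analysis. Section 11.4.2.3 names one test for each type of outcome:

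- End-of-life care: "we will use Fisher's exact test to determine the association between the composite EOL care measure categories and study arm", with risk difference and relative risk as effect measures.
- Utilisation: "we will also compare days on hospice and in the hospital and ICU using the Mann-Whitney U test".
- Survival: "To compare patient survival, we will use Kaplan-Meier estimates, testing the difference between the curves with the log-rank test".

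None of the three mentions a stratum or covariate. The only place where stratification factors enter an analysis is Section 11.3.2, where their use is optional and limited to QOL scores.

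Status. Section 11.4.1.3 groups overall survival with the end-of-life and utilisation endpoints. Section 11.4.2 puts that group third in a sequence tested at 5%. Section 11.2.1 sizes the trial on FACT change only and states no power for these outcomes.

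**The concern.** When allocation is balanced on a factor that predicts outcome, the arms cannot differ much on that factor by chance. An unstratified test still counts the between-stratum variation in its variance. The variance is then too large for the design, so the test rejects too rarely under no effect and misses real effects more often than it needs to.

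The three tests in Section 11.4.2.3 are all those named for Aim 2, on a sample size chosen for another endpoint. Section 1.3 hypothesises survival at least as good as under standard care. A needlessly insensitive test makes a non-significant survival comparison easier to misread as support for that hypothesis.

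**Working it through.** **1. The plan's own figure.** It concerns the primary endpoint: n per arm = 2(1.96 + 0.8416)² × 11.87² / 4² = 138.2, so 139 against the stated 140. Then 140 / (1 − 0.30) = 200. The figure reproduces. There is no corresponding figure for Aim 2.

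**2. Inputs.** From the documents: 400 patients, 1:1; minimisation on both factors; about 300 caregivers for 400 patients (75%, Section 11.2.1); survival follow-up to 3 years (Section 7.4); median survival under one year (Section 1.1). Assumed, because the documents are silent: tumor mix 50/20/30% (lung; esophageal/gastric; hepatic/biliary/pancreatic/unknown), medians by tumor type, hazard ratio 0.75, exponential survival, biased-coin probability 0.8, and no prognostic effect of caregiver participation.

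**3. Log-rank.** Let a be the arm (0/1), e the event indicator and p the proportion of those at risk who are in the palliative care arm. Then U = Σ(a − p)e, V = Σp(1 − p)e, and the test rejects if |U/√V| > 1.96. The stratified test forms U and V within each tumor-by-caregiver cell and adds them. There were 4,000 simulated trials per row.

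| Standard-arm medians (months) | Type I, plain | Type I, stratified | Power, plain | Power, stratified | Gain |
|---|---|---|---|---|---|
| 10/10/10 | 5.4% | 5.9% | 76.8% | 75.4% | −1.4 |
| 12/10/8 | 4.7% | 5.0% | 76.6% | 76.6% | 0.0 |
| 12/9/6 | 3.5% | 4.7% | 73.9% | 76.9% | +3.0 |
| 14/10/5 | 4.1% | 5.5% | 66.3% | 74.9% | +8.6 |

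Monte Carlo standard error: √(0.05 × 0.95 / 4000) = 0.34 points for type I error and √(0.75 × 0.25 / 4000) = 0.68 points for each power. The 5.9% is high by (5.9 − 5.0)/0.34 = 2.6 standard errors. The plain test on the same data sets is also above 5%, so part of the excess is shared chance.

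Analytic check of the first row: with about 353 deaths, power is Φ(√353/2 × |ln 0.75| − 1.96) = Φ(9.39 × 0.2877 − 1.96) = Φ(0.74) = 77%, close to the simulated 76.8%.

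A separate simulation at the same hazard ratio gave gains of about 0 (10/10/10), about 1.5 (12/10/8), 77.6 − 72.1 = 5.5 (11.5/8/5) and 75.5 − 67.6 = 7.9 points (14/10/5). The 11.5/8/5 case keeps every median under one year, as Section 1.1 describes; 14/10/5 does not.

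**4. Binary end-of-life measure.** Assumed: 350 deaths, same mix, odds ratio 1.8; 10,000 runs. An unstratified Pearson test without continuity correction separates two causes. Fisher to Pearson is the cost of exactness; Pearson to Cochran-Mantel-Haenszel (CMH) is the cost of ignoring strata.

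| Stratum rates | Level: Fisher / Pearson / CMH | Power: Fisher / Pearson / CMH | Exactness | Strata |
|---|---|---|---|---|
| 50/50/50% | 3.6 / 4.5 / 4.5% | 73.0 / 76.5 / 76.5% | 3.5 | 0.0 |
| 55/50/40% | 3.6 / 4.5 / 4.7% | 71.2 / 74.9 / 75.8% | 3.7 | 0.9 |
| 65/50/30% | 2.8 / 3.8 / 5.0% | 65.1 / 69.0 / 72.7% | 3.9 | 3.7 |

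**5. Days of care.** Assumed: log-normal outcome, 340 patients, arm effect 0.3 SD on the log scale; 3,000 runs. The van Elteren test sums within-stratum rank sums with weights 1/(n + 1).

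| Stratum shifts | Type I: Mann-Whitney / van Elteren | Power: Mann-Whitney / van Elteren |
|---|---|---|
| none | 5.2 / 5.2% | 75.9 / 76.3% |
| ±0.25 SD | 4.7 / 5.5% | 76.8 / 77.6% |
| ±0.5 SD | 3.5 / 4.8% | 71.9 / 77.3% |

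Real hospital and ICU days will contain many zeros, which this model does not represent.

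**The case against.** The strongest reply is that nothing is broken. The planned tests do not inflate type I error, the outcomes come last in the testing sequence, and much of the secondary analysis is meant to be descriptive. The size depends wholly on figures that the documents do not supply, and with little separation between tumor types there is nothing to recover. A hazard ratio of 0.75 is not a design target either: the hypothesis is survival at least as good, and no power is claimed for it. All of this stands. It limits the point to efficiency.

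Two further objections hold in part. First, some end-of-life measures may be analysed in decedents only, where balance by design is not guaranteed. That weakens the conservatism argument for those measures, but stratifying would then also correct chance imbalance in tumor type. Second, the composite end-of-life categories are not defined as binary, so the binary results are only a guide.

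A reader might also infer that the unstratified analysis biases the survival hazard ratio toward 1. The plan specifies no hazard ratio, and a marginal ratio differs from a stratum-specific one by definition. That reading is not supported.

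**Conclusion.** The point holds as a modest loss of efficiency, conditional on tumor type being prognostic. The direction follows from the design. The size rests on the assumed mix, medians, rates and effects: about 0 to 2 points of log-rank power for little or weak separation, and about 3 to 9 points for moderate to strong separation. The upper end relies on a lung median of 14 months, above the documents' description.

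Two stronger readings should be avoided. One is that the whole gap between Fisher and CMH is due to ignoring strata; 3 to 4 points of it come from Fisher's exactness and would be there with no strata at all. The other is that stratifying is free: at equal medians the six-cell log-rank was 1.4 points lower in one simulation and about level in the other. The trade still favours stratifying, because the possible loss is about 1 point.

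**What to change.** In Section 11.4.2.3, name as main tests:

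- survival: the log-rank test stratified by tumor type;
- end-of-life care: the CMH test, in its general-association form if the composite has more than two categories, with stratified risk difference and relative risk;
- hospice, hospital and ICU days: the van Elteren test stratified by tumor type.

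State whether caregiver participation is added as a stratum by a rule fixed before outcomes are seen, such as a minimum cell size judged on enrolment counts. Under the assumed mix and the plan's 75% caregiver enrolment, the smallest cell would hold about 400 × 0.20 × 0.25 = 20 patients, roughly 10 per arm. Keep the unstratified tests as sensitivity analyses.

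The cost is wording only, since Section 4.7 already has both factors recorded before assignment. The statistical price is about 1 point of power at most if tumor type is not prognostic, and reliance on an asymptotic test in place of an exact one.
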